6.2.4 Handling of Missing or Non-Quantifiable PK Data

For the calculation of individual pharmacokinetic profiles, missing or non-quantifiable (NQ) data will be handled based on the current knowledge of drug pharmacokinetics measures. The methods for missing data imputation will be as follows:

- Missing values will generally be omitted (set to missing) in the derivation of PK parameters and from the individual subject plots.
- A non-quantifiable (NQ) value, and all subsequent NQ values before the first measurable concentration will be set to zero in the derivation of PK parameters, statistical analyses, and the individual subject plots.
- If a single NQ value occurs between measurable concentrations in a profile, the NQ should generally be omitted (set to missing) in the derivation of PK parameters, statistical analysis, and the individual subject plots.
- NQs which occur after the last measurable concentration will be omitted (set to missing) in the derivation of PK parameters, statistical analysis, and from the individual subject plots.

For linear plots, zero concentration value(s) before the first measurable concentration will be included in the plot. For log-linear plots, zero concentration value(s) before the first measurable concentration will be assigned a missing value. Concentration values that are less than lower limit of quantitation (LLOQ) will be indicated on appropriate listings without imputation.

For urine PK parameters, if urine concentration values or volumes are missing, $A_{e(0-24)}$, f_e , and CL_R will not be estimated and will be listed as NA.

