5 STUDY ENDPOINTS

Primary Endpoint

• The primary endpoint is the incidence of adverse events (AEs). Safety will also be evaluated through vital signs, electrocardiograms (ECGs), clinical laboratory assessments, and physical examinations.

Secondary Endpoints

For Part A, the secondary endpoints are:

- PK parameters including, but not limited to, maximum plasma concentration [C_{max}], time to reach maximum plasma concentration [t_{max}], area under the plasma concentration versus time curve [AUC], apparent terminal elimination half-life [t_½], fraction eliminated in urine [fe/F], and renal clearance [CL_R]
- Plasma and urine glycolate concentration

For Part B, the secondary endpoints are:

- First dose and steady state PK parameters including, but not limited to, C_{max} , t_{max} , AUC, $t_{1/2}$, fe/F, and CL_R
- Urinary oxalate excretion (oxalate content in 24-hour urine collection)
- Urinary glycolate excretion (glycolate content in 24-hour urine collection)
- Plasma glycolate concentration
- Calculated creatinine clearance

Exploratory Endpoints

The exploratory endpoints are:

- Plasma oxalate concentration
- I lasma oxalate concentration

Additional exploratory endpoints for Part B only are:

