6.2.2 PK Parameters

In Part A, PK parameters following single dose of ALN-GO1 (Day 1) will be characterized. In Part B, PK parameters following single and multiple doses (Day 1 and Day 57 for monthly dosing cohorts; Day 1 and Day 85 for quarterly dose cohorts) of ALN-GO1 will be calculated.

The following PK parameters will be calculated from the individual plasma concentration profiles ALN-GO1 by standard non-compartmental methods:

Parameters	Units	Description
C_{max}	ng/mL	Maximum observed plasma concentration
t_{max}	h	The time to reach the maximum observed concentration
AUC ₀₋₂₄	ng·h/mL	The area under the plasma concentration versus time curve, from time 0 to the 24 hour concentration (C_{24h}), as calculated by the linear trapezoidal method
AUC _{0-last}	ng·h/mL	The area under the plasma concentration versus time curve, from time 0 to t _{last} (time of last quantifiable concentration) as calculated by the linear trapezoidal method.
AUC _{0-inf}	ng·h/mL	The area under the plasma concentration versus time curve, from time 0 extrapolated to infinity, calculated as: $AUC_{0-inf} = AUC_{0-last} + C_{last}/\lambda z$ (Reported for Part A only)
AUC _{tau,ss}	ng·h/mL	Steady state area under the plasma concentration versus time curve, over the dosing interval at steady state (Reported for Part B only)
Lambda z (λ_Z)	h ⁻¹	Apparent terminal elimination rate constant calculated by linear regression of the terminal linear portion of the log concentration versus time curve
t _{1/2}	h	Apparent terminal elimination half-life, calculated as: $ln(2)/\lambda_Z$
CL/F	L/h	Total apparent body clearance after extravascular administration, calculated as: Dose/AUC _{0-inf}
CL/Fss	L/h	Total apparent body clearance at steady-state after extravascular administration, calculated as: Dose/AUC _{0-tau} (Reported for Part A only)
V _Z /F	L	Apparent volume of distribution based on the terminal elimination phase, calculated as: Dose/(AUC _{0-inf} × λ_Z) (for Part A) or Dose/(AUC _{0-tau} × λ_Z) (for Part B)

The following urine PK parameters will also be calculated:

Parameters	Units	Description
A _{e(0-24)}	mg	Cumulative amount of drug excreted in urine after dosing, calculated as the sum of $(C_{ur} \times V_{ur})$, where C_{ur} is the concentration in urine and V_{ur} is the volume of urine collected.
fe/F	%	Fraction eliminated in the urine, calculated as $(A_{e(0\text{-}24)}/Dose) \times 100$
CL_R	L/h	Renal clearance, calculated as A _{e(0-24)} /AUC ₀₋₂₄

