6.2.3 Pharmacokinetic Parameter Calculation

Actual sampling times, rather than scheduled sampling times, will be used in all computations involving sampling times.

The PK parameters λ_z , $t_{1/2}$, AUC_{0-inf} , CL/F, and V_z/F will not be presented for those subjects who do not exhibit a terminal elimination phase in their concentration versus time profiles. In order to estimate the apparent first-order terminal elimination rate constant, λ_z , linear regression of concentration in logarithm scale vs. time will be performed using at least 3 data points. Uniform weighting will be selected to perform the regression analysis to estimate λ_z . The constant λ_z will not be assigned if:

- The terminal elimination rate constant indicates a positive slope ($\lambda_z < 0$)
- T_{max} is one of the last 3 data points
- The adjusted regression coefficient (R²) is less than 0.8
- $t_{1/2}$ is more than half the total sampling interval

In cases where the λ_z interval is not assigned, the values of the associated parameters (λ_z , $t_{1/2}$, AUC_{0-inf} , CL/F, V_z/F , and possibly AUC_{0-24h}) will not be reported.

The linear trapezoidal method will be used in the computation of all AUC values. AUC_{0-inf} will be calculated as $AUC_{0-last} + C_{last,observed}/\lambda_z$, where $C_{last,observed}$ is the last observed evaluable plasma concentration.

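### Read literally, SAP 6.2.4 turns a collected urine pool below the quantitation limit into a missing value, and so removes Ae(0-24), fe/F and renal clearance for that dosing occasion

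*SAP*

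**What the plan says.** SAP section 6.2.4 covers missing and NQ PK data together. Its NQ rules depend on where the NQ falls:

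- **Leading:** a first NQ and "all subsequent NQ values before the first measurable concentration will be set to zero in the derivation of PK parameters".
- **Between:** a single NQ between measurable values is generally set to missing.
- **Trailing:** "NQs which occur after the last measurable concentration will be omitted (set to missing) in the derivation of PK parameters".

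The section closes with a urine sentence: "For urine PK parameters, if urine concentration values or volumes are missing", then Ae(0-24), fe and CL_R "will not be estimated and will be listed as NA". It makes no exception for NQ.

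SAP 6.2.2 lists these three as urine PK parameters. Ae(0-24) is the sum of concentration times volume over the collections, fe/F is Ae(0-24) as a percentage of dose, and CL_R is Ae(0-24) divided by AUC0-24. SAP section 5 names fe/F ("fraction eliminated in urine") and CL_R among the secondary PK endpoints for both parts.

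Protocol Appendix 11.1 gives the pools: 0-4, 4-8 and 8-24 h in Part A (Table 10), and 0-4, 4-8, 8-12 and 12-24 h in Part B (Tables 11 and 12).

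**The concern.** Dropping trailing NQs is a normal convention for a plasma curve, where AUC0-last stops at the last quantifiable point. It does not suit a cumulative sum over pools. A urine pool that was collected, measured for volume and assayed below the LLOQ tells us that little drug was excreted in that interval. Treating it like a pool that was never collected discards that information, and also the earlier pools where the drug was quantified.

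The loss would also depend on the result. Subjects with low late urine concentrations, from a low dose, low excretion or fast elimination, would go to NA first. The fe/F and CL_R summaries would then describe the subjects with more late excretion, and comparisons across doses would be affected.

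**Working it through.** The plan states no figure that depends on this rule, so there is none to reproduce. The check applies the rules to example profiles and then bounds the cost of the alternative.

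**1. Chain of rules**
- The trailing-NQ rule acts whenever PK parameters are derived and names no matrix (6.2.4).
- Ae(0-24), fe/F and CL_R are listed as urine PK parameters (6.2.2).
- Ae(0-24) is a sum over all pools, so one missing pool leaves it undefined.
- The urine sentence then makes all three NA (6.2.4).

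**2. Literal application to a hypothetical Part A subject**

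From the documents: lowest dose 0.3 mg/kg (Protocol 4.7.1) and three pools. Assumed: 70 kg, so the dose is 0.3 x 70 = 21 mg; pool volumes 400, 400 and 1200 mL; and the concentrations shown.

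Ae = sum(C x V)/10^6 mg, with C in ng/mL and V in mL. fe/F = 100 x Ae/21.

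| Pools (ng/mL) | Values after the NQ rules | Ae (mg) | fe/F |
|---|---|---|---|
| 2000, 500, 30 | unchanged | 0.8 + 0.2 + 0.036 = 1.036 | 4.93% |
| NQ, 500, 30 | 0, 500, 30 | 0.2 + 0.036 = 0.236 | 1.12% |
| 2000, 500, NQ | 2000, 500, missing | NA | NA |
| 2000, NQ, NQ | 2000, missing, missing | NA | NA |

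An early NQ pool keeps the subject and a late one removes the subject. If the leading rule is extended to a subject with every pool NQ, fe/F is 0 and is kept, while a subject with measurable early excretion is lost.

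**3. What the NQ pool could hold**

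The most it can hold is LLOQ x V, so its share of dose is at most 100 x LLOQ x V/dose. The documents give no urine LLOQ; 1-100 ng/mL is assumed. Per litre (1000 mL) and 21 mg:
- 1 ng/mL: 0.001 mg, 0.005% of dose
- 10 ng/mL: 0.01 mg, 0.05%
- 100 ng/mL: 0.1 mg, 0.48%

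For the subject with 2000, 500, NQ, counting the last pool as zero gives Ae = 1.0 mg and fe/F = 4.76%. Counting it at the full LLOQ over 1200 mL gives 4.77%, 4.82% or 5.05% for an LLOQ of 1, 10 or 50 ng/mL. At 50 ng/mL the bound is 0.06/1.06 = 5.7% of Ae. The error is therefore small against dose but not always against a small Ae, which is why the bound should be listed.

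**The case against.** The strongest reply is that the NQ rules were meant for plasma. They are introduced as rules for individual profiles and refer to individual subject plots; SAP 6.2.2 uses the word profiles for plasma, and SAP 7.5 plans concentration plots for plasma only. Urine has its own sentence, triggered by missing values, and 6.2.4 treats missing and NQ values in separate bullets. On that reading NA already applies only to absent samples or volumes. This is plausible, so the loss cannot be called a demonstrated error. But the SAP does not say it, and an NQ urine pool would then have no rule at all. The same clarification is needed either way.

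Three stronger inferences are tempting and do not stand:

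- **A known size of loss or bias.** With first-order excretion, an assumed fe of 20%, a 21 mg dose and a 1 h half-life, simulation keeps 89% down to 8% of subjects as the assumed LLOQ goes from 1 to 100 ng/mL. With a 3 h half-life and an LLOQ of 10-50 ng/mL it keeps at least 99%. The documents fix none of these inputs, so such figures show only that the answer is open.
- **Part B groups of only 3.** That is the blinded active arm. SAP 7.5 combines blinded and open-label PK data by dose level, and the combined groups in 7.2.3 are 4 or 8 (monthly) or 4 (quarterly).
- **CL_R also lost through plasma.** AUC0-24 is defined to the 24 h concentration, but 6.2.3 lists it only as possibly unreported when lambda-z is not assigned, so an NQ at 24 h does not by itself produce NA. Substituting AUC0-last would be unsound: Part A plasma is not sampled between 8 and 24 h (Table 10), so the omitted area depends on the 8 h value and not on the LLOQ. Assuming one compartment, ka 1/h and a 3 h half-life, AUC0-8 is about 80% of AUC0-24, and CL_R would be overstated by about 1/0.80 - 1 = 25%.

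It is also fair that the analyses are descriptive, that the primary endpoint is adverse events, and that individual urine concentrations are listed (SAP 7.5), so the NQ pattern would remain visible.

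**Conclusion.** The concern holds as a conditional consequence of the text. Applied literally, 6.2.4 makes Ae(0-24), fe/F and CL_R NA for a dosing occasion when a collected late pool is NQ, and generally also when a single NQ pool lies between measurable ones. This removes two named secondary endpoints in a way that depends on the result, although the pool's content is known to lie between zero and LLOQ x volume.

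How often it would happen, and how far summaries would shift, cannot be judged from the documents. The direction is clearer: the loss is likeliest at low doses or with fast elimination. The conclusion assumes that the NQ rules govern urine, which the text permits but does not state. Only these derived parameters are lost; the subject's other data are unaffected.

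**What to change.** In SAP 6.2.4, state that:

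1. the rules setting NQ values to missing do not apply to urine pools;
2. a collected post-dose urine pool reported NQ contributes zero to Ae(0-24), and LLOQ x volume is listed as its upper bound;
3. NA applies only when a urine sample or its volume was not obtained.

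This takes two or three sentences and changes no study procedure. The cost is a small downward error in Ae(0-24) and fe/F. In fe/F it is at most LLOQ x volume/dose for each NQ pool, which is the 0.005-0.5% per litre at 21 mg shown above and proportionately less at higher doses. CL_R carries the same relative error as Ae(0-24). The listed bound lets a reader see where that error is not negligible.

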6.3 Pharmacodynamics Assessments

Urine and blood samples will be collected for assessment of PD parameters (oxalate and glycolate concentrations) at the time points in the Schedule of Assessments for Part A and Part B.

In Part B, 24-hour urine collections will be analyzed for glycolate, oxalate, and creatinine excretion. The 24-hour urine collection starting on Day -1 must conclude on Day 1 before administration of the first dose of study drug. PD blood samples will also be collected prior to dosing for the analysis of plasma glycolate and oxalate concentration.

For Part A, baseline for PD parameters is defined as the last non-missing measurement prior to the first dose of randomized study drug.

For Part B, baseline is defined as the median for 24-hour urine PD parameters of the measurements and as the mean for all other PD parameters of the measurements during the screening period prior to the first dose date/time of study drug in the study. Patients randomized to placebo will receive open-label ALN-GO1 after their single-blind placebo dosing period. Baseline for the open-label ALN-GO1 dosing period for these patients will be the median or mean of all assessments after the single-blind placebo first dose date/time and prior to the open-label ALN-GO1 first dose date/time for 24-hour urine PD parameters or all other PD parameters, respectively.

The following PD parameters will be assessed in Part A:

- Plasma glycolate concentration
- Urine glycolate concentration
- •
- •

The following PD parameters will be assessed in Part B:

- Plasma glycolate concentration
- Urine glycolate concentration
- Plasma oxalate concentration

- Urine oxalate concentration
- 24-hour urine oxalate content corrected for BSA
- 24-hour urine creatinine content
- 24-hour urine oxalate/creatinine ratio
- 24-hour urine glycolate content

6.4	Exploratory Assessments
•	
•	
•	
•	
•	
•	
•	
•	
•	
•	
•	

6.5 Immunogenicity

Blood samples will be collected to evaluate antidrug antibodies (ADA). Blood samples for ADA testing that are collected on the day of dosing must be collected before study drug administration. Blood samples to evaluate ADAs will be collected throughout the treatment and follow-up periods as detailed in the Schedule of Assessment. Confirmed positive ADA samples will be tested for cross-reactivity with DNA and nucleic acids.

7 STATISTICAL ANALYSIS

This study is designed to evaluate the safety, tolerability, PK, and PD of single- and multiple-ascending doses of ALN-GO1. The described analyses will be carried out separately for Part A and Part B of this study.

Statistical analyses will be primarily descriptive and no formal hypothesis testing will be performed in this study. Assessments of change from baseline to post-treatment will be computed only for those subjects with both baseline and post-treatment measurements.

7.1 Analysis Periods in Part A

Part A is the single ascending dose study part. Subjects will be randomized in a 3:1 ratio (ALN-GO1: placebo) to receive 1 dose of a single-blind study drug and followed until Day 57/End of Treatment (EOT). If additional follow-up beyond Day 57 (End of Treatment) is required, this will be defined as the safety and PD follow-up period.

In Part A, summary statistics for Safety and PD data will be presented by ascending dose level of ALN-GO1 and the pooled placebo group with pooled placebo presented first. The pooled placebo group includes subjects receiving placebo across all cohorts.

7.2 Analysis Periods and By-visit Data Presentation in Part B

Part B is the multiple ascending dose study part including monthly and quarterly dosing regimens with ALN-GO1 or placebo. Analysis periods and treatment groups will be defined in Section 7.2.1 and Section 7.2.2.

All data listings will be presented with corresponding treatment, study day relative to first dose date of study drug, and study day relative to first dose of ALN-GO1.

7.2.1 Single-Blind Dosing Period

In Part B, Safety and PD data during the single-blind period will be summarized for the period starting from the first single-blind study drug date/time up to, and including, Study Day 85 for patients randomized to ALN-GO1, or prior to the first dose of ALN-GO1 for patients randomized to placebo. Patients receiving placebo in all regimen and dose cohorts will be pooled together.

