Review/record AEs ^y			X																		
Prior and concomitant medications		X																			

Abbreviations: ADA=antidrug antibodies; AE=adverse event; BMI=body mass index; D=day; ECG=electrocardiogram; Echo=echocardiography; eGFR=estimated glomerular filtration rate; EOT=end of treatment; FSH=follicle-stimulating hormone; ICF=informed consent form; LFT=liver function test; PD=pharmacodynamics; PK=pharmacokinetic; Q=every; SC=subcutaneous.

Notes:

- When scheduled at the same time points, the assessments of vital signs and 12-lead ECGs must be performed first, before the physical examinations, blood sample collections, and urine collections.
- Assessments should be performed predose, where applicable, unless otherwise noted.

- Grey columns indicate the study day when the 24-hour urine collection for PD analysis should begin. Patients may be admitted to the clinical study center to complete the 24-hour urine collections.
 - a. Patients will be invited to participate in an open-label extension study once they complete the postdose follow-up period on Study Day 141. For patients who do not enroll in the open-label extension study, safety and PD follow-up will continue until plasma glycolate is <20% above baseline or \leq the ULN AND 24-hour urinary oxalate is >80% of baseline, or until the SRC makes a decision per investigator request to discontinue follow-up on a case-by-case basis. The decision cannot be made until after completion of the postdose follow-up period (84 days after last dose).
 - b. Patients initially randomized to placebo may continue in the study receiving administration of open-label ALN-GO1 according to the Schedule of Assessments (Table 3). Patients will be unblinded on or after Day 78.
 - c. Complete medical history (including documentation or confirmation of PH1) will be obtained at screening and any changes will be updated on Day -1. AEs occurring after signing of the ICF and before study drug administration will be captured as medical history.
 - d. See Section 7.5.3 for assessments to be performed during a full physical examination or symptom-directed physical examination.
 - e. During screening and at EOT, height will be measured for all patients; thereafter, height will only be measured for patients <18 years of age. Additionally, for patients <18 years of age, at each time point, height will be measured in centimeters, and in triplicate, to facilitate calculation of eGFR using the Schwartz Bedside Formula.

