5.3.1. Discontinuation of Study Drug

The Investigator or designee may discontinue dosing in a subject/patient if the subject/patient:

- Is in violation of the protocol
- Experiences a serious or intolerable AE
- Requires a prohibited medication
- Becomes pregnant
- Is found to be noncompliant with the protocol-requirements in a manner that is considered by the Investigator to compromise patient safety and/or the integrity of the study

The Investigator will confer with the Sponsor, or Medical Monitor, before discontinuing dosing. Subjects/Patients who are pregnant will be discontinued from dosing immediately (see Section 7.5.7.6 for reporting and follow-up of pregnancy). Subjects/patients who discontinue study drug may be replaced (see Section 5.3.3). Subjects/patients who discontinue study drug dosing for any reason will be encouraged to complete the remaining assessments through the remaining scheduled study visits so that their experience is captured in the study analyses. Subjects/Patients who discontinue study drug but who agree to attend the remaining scheduled study visits will not be considered withdrawn from study. Such subjects/patients may receive local standard of care treatment for their disease, as applicable.

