8.2. Statistical Methodology

A Statistical Analysis Plan (SAP) will be finalized before database lock. The plan will detail the implementation of all planned statistical analyses in accordance with the principal features stated

in the protocol. Any changes to the methods described in the final SAP will be described and justified as needed in the clinical study report.

Statistical analyses will be primarily descriptive. Analyses will be performed using SAS[®] (Version 9.2, or higher). Data from Parts A and B will be analyzed separately. Tabular summaries will be generated by dose level and dosing regimen of ALN-GO1 and placebo (pooled across all cohorts) for Part A and Part B (through Day 85).

Safety and PD data will be summarized by dose level and dosing regimen of ALN-GO1 compared to placebo for data collected up to, and including, study Day 85. Data from placebo patients from all cohorts will be combined. Data collected after Day 85 will be summarized separately for patients in quarterly dosing cohorts who receive a second dose of ALN-GO1 on Day 85. Additionally, all safety and PD data collected from all patients in Part B during the ALN-GO1 dosing period, regardless of treatment sequence, will be combined and summarized by ALN-GO1 dose level and regimen.

Data collected beyond the designated dosing period will be summarized or presented in data listings.

Descriptive statistics will be presented for continuous variables. Frequencies and percentages will be presented for categorical and ordinal variables. Percentages will be based on the number of non-missing values in a dose group.

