7.4.1 Adverse Events

In Part A, summary tables for AEs will be presented by ascending ALN-GO1 dose level, in total with all subjects receiving ALN-GO1, and placebo with subjects/patients receiving placebo pooled across enrollment cohorts presented first. AEs will be summarized separately for the single-blind dosing period and the study.

In Part B, for patients who were randomized to placebo, an AE during the single-blind period is defined as an AE with onset date/time on and after the first dose date/time of placebo and prior to the first dose date/time of open-label ALN-GO1. For patients who were initially randomized to ALN-GO1 a AE during the single-blind period is defined as an AE with onset date/time on or after the first dose date/time of ALN-GO1 and up to, and including, Study Day 85. AEs for single-blind period will be summarized by regimen and ascending dose level of ALN-GO1 and pooled placebo across regimen and dose being presented first. Sub-total for each regimen and overall will also be presented.

In Part B, a summary of AEs for the single-blind period will be provided by regimen and ascending dose level of ALN-GO1 and pooled placebo presented first. Total for each regimen and overall of ALN-GO1 will also be provided.

In Part B, for all patients receiving ALN-GO1, either as single-blind or open-label administration, and in any sequence, a AE is defined as an AE with onset date/time on or after the first dose date/time of ALN-GO1 and up to the end of study. All AEs under ALN-GO1 will be summarized by regimen and ascending dose, sub-total for each regimen, and for overall. At each dose level and for the sub-total and overall, AEs with be summarized for patients with single-blind administration only and then for single-blind and open-label administration combined.

In each analysis above, an overview of adverse events will be provided which summarizes subject-level incidence (frequency) of all AEs, drug-related AEs, grade 3/4/5 AEs, drug-related grade 3/4/5 AEs, treatment-emergent SAEs, drug-related treatment-emergent SAEs, and AEs leading to discontinuation of study drug and/or deaths.

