7.4.2 Dosing and Extent of Exposure

The actual dose administered and the number of injections will be summarized descriptively by dose level (or placebo) and overall for the Safety Analysis Set in Part A. Compliance with study drug administration is not relevant as all doses will be administered by qualified clinical study site personnel and recorded on the electronic Case Report Form.

Part B consists of three doses of study drug on Days 1, 29, and 57 for monthly dosing cohorts. For patients who randomized to placebo and crossed over to ALN-GO1 during the open label portion, study drug will be administered on Days 85, 113, and 141. Patients who randomized to receive ALN-GO1 will receive study treatment in a single-blind manner while patients enrolled in expansion cohorts will receive ALN-GO1 in an open-label manner.

In Part B for quarterly dosing cohorts, patients will receive either ALN-GO1 or placebo according to the randomized treatment assignment on Day 1. All patients in quarterly dosing cohorts, including those randomized to placebo, will receive open-label ALN-GO1 on Day 85 at the same dose administered to the cohort into which they were initially randomized.

Treatment duration of study drug in Part B is defined as:

- For patients randomized to placebo in monthly or quarterly cohorts, treatment duration of placebo is min (first dose date of open-label ALN-GO1 or visit date of Day 85 visit) – first dose date of placebo +1
- For patients in monthly dosing regimen, treatment duration of ALN-GO1 is the visit date of Day 85 relative to first dose of ALN-GO1 first dose date of ALN-GO1 +1
- For patients randomized to placebo in quarterly dosing cohorts, their treatment duration of open-label ALN-GO1 is the same as for monthly dosing regimen.

• For patients randomized to ALN-GO1 in quarterly dosing cohorts, the single-blind treatment duration is Day 85 visit date – first dosed date of ALN-GO1 +1 and the total ALN-GO1 treatment duration is Day 169 visit date – first dose date of ALN-GO1 +1.

Treatment duration of study drug will be summarized using descriptive statistics by regimen, ascending dose level of ALN-GO1, pooled placebo, and in total for the single-blind time period and total ALN-GO1 dosing period.

In Part B, dosing status will be tabulated by regimen and dose level (including placebo during the summary for the single-blind study period). The following categories will be summarized:

- Subjects with a missed dose,

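### The Part B single-blind adverse event window closes at Day 85 for ALN-GO1 but has no Day 85 limit for placebo patients who cross over late or not at all

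*SAP*

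**What the plan says.** SAP 7.2.1 starts the Part B single-blind period at the first single-blind dose and runs it to "Study Day 85 for patients randomized to ALN-GO1, or prior to the first dose of ALN-GO1 for patients randomized to placebo". SAP 7.4.1 applies this to AEs. A placebo patient's event counts if its onset is "on and after the first dose date/time of placebo and prior to the first dose date/time of open-label ALN-GO1". An ALN-GO1 patient's event counts if its onset is "on or after the first dose date/time of ALN-GO1 and up to, and including, Study Day 85".

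Three other places stop placebo data at Day 85:

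- Protocol 8.2 summarizes safety and PD data by ALN-GO1 dose level and regimen "compared to placebo for data collected up to, and including, study Day 85".
- SAP 7.2.3 restricts by-visit placebo summaries to Days 1 to 85 and marks later placebo cells as not applicable.
- SAP 7.4.2 takes the earlier of two dates for exposure: "treatment duration of placebo is min (first dose date of open-label ALN-GO1 or visit date of Day 85 visit".

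SAP 9 declares no change from the protocol's analysis.

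On crossover, Protocol 1.3 intends all Part B patients to receive active drug. For monthly cohorts, however, Protocol Table 2 footnote b reads "Patients initially randomized to placebo may continue in the study receiving administration of open-label ALN-GO1". Protocol 5.3.1 adds "Subjects/patients who discontinue study drug dosing for any reason will be encouraged to complete the remaining assessments", and those who agree to attend are not treated as withdrawn. AEs are recorded through the end of the study (Protocol 7.5.7.2, SAP 6.1.1).

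**The concern.** The AE rule gives the two arms different stopping conditions: a calendar cut for ALN-GO1 and a dosing event for placebo. If the dosing event does not happen, the placebo window has no end. The patient's later events also have no other home, because every follow-up period in SAP 7.2.2 is counted from the first ALN-GO1 dose.

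A missed or late crossover is possible under the plan. Monthly crossover is worded as optional. Protocol Table 7 stops dosing in an individual after certain events. Under Protocol Table 8, a related Grade 4 or 5 event suspends dosing of all Part B patients, which could delay a placebo patient's first ALN-GO1 dose.

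AE incidence is the primary endpoint, and the single-blind summary is the only placebo comparison of AEs in Part B. The asymmetry can only lengthen placebo observation, so any distortion raises the placebo percentages. The earlier-of rule in SAP 7.4.2 shows that a placebo patient without a timely ALN-GO1 dose was foreseen for exposure, but the same limit was not carried into the AE definition.

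**Working it through.** There is no power or alpha figure to reproduce; the analysis is descriptive. The plan's figure that matters here is the placebo group size.

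**Placebo N.** Cohorts of 4 randomized 3:1 (Protocol 4.1.2) give 4 × 1/4 = 1 placebo patient each. The SAP 7.2.3 shells show two monthly and two quarterly dose levels, so 4 × 1 = 4, which matches their N=4. Two planned plus three optional cohorts would give 5.

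**Window per patient.**

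- ALN-GO1: Days 1 to 85, 85 days.
- Placebo, crossing over on Day 85: about 84 days.
- Placebo, monthly, never crossing, followed to the end of postdose follow-up in Protocol Table 2 (Day 141): 141/85 = 1.66 times, 56 days more.
- Placebo, quarterly, never crossing, followed to the end of postdose follow-up in Protocol Table 4 (Day 169): 169/85 = 1.99 times, 84 days more.

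**Pooled placebo AE-days with one non-crosser.** As written: (N − 1) × 84 + last day. With a Day 85 cap: (N − 1) × 84 + 85.

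| N | Capped | To Day 141 | To Day 169 |
|---|---|---|---|
| 4 | 337 | 393 (+17%) | 421 (+25%) |
| 5 | 421 | 477 (+13%) | 505 (+20%) |

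**Expected shift in pooled placebo incidence.** The documents give no AE risk, so take an assumed 85-day risk p between 0.2 and 0.8 and a constant hazard. The non-crosser's risk by day d is 1 − (1 − p)^(d/85). The pooled shift is that risk minus p, divided by N.

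| p | Risk by Day 141 | Shift, N=4 | Shift, N=5 | Risk by Day 169 | Shift, N=4 | Shift, N=5 |
|---|---|---|---|---|---|---|
| 0.2 | 0.309 | 2.7 points | 2.2 | 0.358 | 4.0 points | 3.2 |
| 0.4 | 0.571 | 4.3 | 3.4 | 0.638 | 5.9 | 4.8 |
| 0.6 | 0.781 | 4.5 | 3.6 | 0.838 | 6.0 | 4.8 |
| 0.8 | 0.931 | 3.3 | 2.6 | 0.959 | 4.0 | 3.2 |

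**Realised table.** A row either does not move or moves by one patient: 1/4 = 25 points or 1/5 = 20 points.

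**The case against.** The case on the other side is substantial, and most of it limits the reach of the point.

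- *Crossover is the design.* Protocol 1.3 says so, and the quarterly footnote (Protocol Table 4, footnote b) states it without the optional wording. With on-time crossover nothing is unbalanced, and with 4 or 5 placebo patients the gap may never open. This stands.
- *By-visit tables are already capped* by SAP 7.2.3. This stands. What remains is AEs and other summaries that are not by visit, such as the worst-value laboratory shift tables.
- *Incidence counts each patient once* per system organ class and preferred term (SAP 7.4.1). A reader might infer that the rule inflates the overall AE and SAE rows, because patients stopped for severe events are the ones who do not cross over. The documents do not support that. A patient with such an event before Day 85 is already in the any-AE and high-grade rows, and in the SAE row if it was serious. Longer follow-up adds mainly new term rows or a worse grade. Nor does Protocol Table 7 say that stopping placebo bars later open-label dosing.
- *Very long windows.* A reader might take the monthly study time of up to 462 days, subtract 45 days of screening and arrive at Day 417. That figure is an upper estimate. Extended follow-up ends once oxalate and glycolate meet the recovery criteria in Protocol 4.1.2, which a patient given only placebo may already meet. Even Days 141 and 169 assume attendance at the remaining visits. The minimum is 84 days after the last dose, so stopping after Day 1 or Day 29 could end follow-up at Day 85 or Day 113.
- *Hiding an excess on ALN-GO1.* A reader might infer this too. But SAP 7.4.1 also tabulates all AEs on ALN-GO1 to the end of the study, the listings carry study day and a single-blind flag, and the safety committee works unblinded.
- *Exposure mismatch.* No exposure-adjusted AE rate is planned, so the SAP 7.4.2 duration never serves as an AE denominator.

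None of this supplies the missing end date or removes the conflict with Protocol 8.2 and SAP 7.4.2.

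**Conclusion.** The point holds in a narrow form. SAP 7.4.1 and 7.2.1 state a rule that gives unequal AE windows whenever a placebo patient crosses over late, or does not cross over and remains in follow-up. It departs from the protocol's Day 85 comparison although SAP 9 declares no departure.

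For one monthly non-crosser followed to Day 141, with 4 placebo patients, the expected shift is about 3 to 5 points; for a quarterly non-crosser followed to Day 169 it is about 4 to 6. These figures rest on an assumed 85-day risk of 0.2 to 0.8, a constant hazard, and full attendance to those days. An actual row moves by 20 to 25 points or not at all. The frequency of missed or late crossover is not in the documents, so the chance that the rule matters cannot be estimated.

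The analysis is descriptive, so no error rate is affected. The consequence is a placebo column that may not cover the period the protocol specifies for it.

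**What to change.** In SAP 7.4.1 and 7.2.1, end the placebo single-blind period at the earlier of (a) just before the first ALN-GO1 dose and (b) the same Study Day 85 cut used for the ALN-GO1 arm. This agrees with Protocol 8.2 and follows the logic of SAP 7.4.2. Leave the by-visit Day 85 assessment, with its visit window, under SAP 7.2.3, so that a Day 85 visit held a little late is not dropped. List separately the later events of placebo patients who have not received ALN-GO1.

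The cost is one sentence in each of two sections, a line of programming and one listing. No new data are needed, and no result changes if every placebo patient crosses over on time.
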